4.2 Inclusion criteria

In order to be eligible to participate in this study, a subject must meet all of the following criteria:

- Patients 18 years and older
- Dutch or English speaking patients
- Patients with an acute complete UCL rupture, with or without a Stener Lesion, diagnosed using physical examination, performed by the hand surgeon. When providing radically directed force to the proximal phalanx (radial deviation stress) as the thumb metacarpal is stabilized in a neutral position, criteria 1 AND 2 must be present to confirm the diagnosis of a complete UCL rupture:
 - no firm endpoint in the MCP joint AND
 - at least more than 35 degrees of laxity in the MCP joint, measured with the MCP joint in 30 degrees of flexion OR more than 15 degrees difference in laxity compared with the uninjured side.

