During the first presentation at the outpatient clinic the surgeon (with sufficient experience in treatment of UCL injuries) confirms the diagnosis complete UCL rupture by physical examination. Laxity of the MCP joint is examined by providing radial force to the proximal phalanx, while stabilizing the thumb metacarpal bone. Stressing the MCP joint in the acute setting may be painful and quarding or muscle spasm may give a false-negative examination. Local anesthesia can be injected into the MCP joint to allow for better examination, when indicated. When the diagnosis of a complete UCL rupture is confirmed (according to the criteria provided under the inclusion criteria), the patient meets the inclusion criteria and has provided informed consent, the patient is randomized. Baseline outcome measures are evaluated in the form of surveys. If feasible at the study site, an ultrasound of the thumb is planned prior to application of a new cast to confirm the diagnosis for study purposes. The outcome of the ultrasound is blinded for the patients as well as for the surgeon. A new cast to immobilize the MCP, in 10-30 degrees (slight) flexion (neutral position), and the CMC joint, in 30-40 degrees palmar abduction, is applied (IP joint is free). Patients will be immobilized for a total period of 4 weeks, including the period between ED and outpatient clinic. After 4 weeks the immobilization cast will be replaced by a removable cast for a period of 4 weeks. Two weeks after the start of immobilization, a second appointment is scheduled to repeat examination of the thumb.

3) Repeat examination at the hand surgery outpatient clinic 2 weeks after ED visit. Laxity of the MCP joint is re-examined by a hand surgeon. The hand surgeon examines if 'tightening' of the UCL has occurred by applying radial deviation stress to the dumb. The chance that re-examination at 2 weeks will induce a re-rupture or a Stener Lesion is close to zero, as re-examination at this time is also part of the current clinical practice in case of

V7 01-02-2024 14 of 30

cast immobilization. 'Tightening' is not a subtle finding and might even be present with less opening during radial deviation stress when compared to the contralateral thumb.

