5.2 Summary of findings from clinical studies

Two systematic reviews are available on the treatment of complete UCL ruptures. [8,9] Both studies investigated nonoperative and operative treatment of patients with an acute complete tear of the UCL and concluded that no studies directly comparing nonoperative treatment with operative treatment were present. Regarding the current evidence, nonoperative treatment of complete UCL ruptures, including Stener Lesions, has been shown to be effective in most patients. [2,3] Although the ligament sometimes heals with slight laxity, there is no evidence for any benefits to surgery that outweigh the risks of nonoperative treatment.

Pichora et al observed 32 patients with a complete tear, with and without Stener Lesions, treated with bracing for 1 year. [2] Final laxity measured 2.3° on average; 91% of patients either felt normal or had minimal disability. Functional outcomes such as motion, timed dexterity, and grip and pinch strength measured 89% to 99% of the uninjured side. Three patients required secondary surgery. Landsman et al reported 6 out of 40 patients treated nonoperatively (15%) requested surgery, although they included several bony avulsions. [3]

The proposed intervention for complete UCL ruptures, including Stener Lesions, is a trial of cast immobilization with repeat examination after 2 weeks. There is no evidence that suggests that such a delay negatively affects the outcome if surgery is needed. Thumb immobilization of a complete tear is well described and frequently a successful method of treatment. However, qualitative, focused studies comparing cast immobilization with operative treatment are lacking.

V7 01-02-2024 17 of 30

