Range of motion (ROM): flexion and extension of the metacarpophalangeal (MCP) joint and interphalangeal joint (IP) and palmar abduction of the carpometacarpal (CMC) joint are measured with a goniometer. The first measurement is performed at both sides. ROM is measured from the moment the patient is allowed to move the MCP joint; after 4 weeks of immobilization (when the immobilizing cast is replaced by a removable cast) and at 3, 6, and 12 months.

Kapandji-score is used for assessing the opposition of the CMC joint. The opposition test consists of touching the four long fingers with the tip of the thumb. The more the tip of the thumb is able to oppose to the base of the pink, the higher the score will be. [12] The first measurement is performed at both sides. Kapandji score is measured from the moment the patient is allowed to move the MCP joint after 4 weeks of immobilization (when the immobilizing cast is replaced by a removable cast) and at 3, 6, and 12 months.

V7 01-02-2024 19 of 30

Grip strength: measured with a hand-held dynamometer. The measurement includes three trials of maximum grip force using the second handle of a calibrated dynamometer, with the elbow in 90° flexion. Dynamometer settings will be on setting two for all patients. Each center will use the same type of dynamometer. The mean score of three trials will be used for analysis as an absolute measure. Grip strength is measured at 3, 6, and 12 months. The first measurement is performed at both sides.

Pinch strength: key pinch/lateral pinch and tip pinch will be measured. Key pinch includes three trials of maximum force between the radial side of the index finger and the pulp of the thumb, using a calibrated pinch gauge, with the elbow in 90° flexion. Tip pinch includes three trials of maximum force between the tip of the index finger and the tip of the thumb, using a calibrated pinch gauge, with the elbow in 90° flexion. Each center will use the same type of pinch gauge. The mean score of three trials will be used for analysis as an absolute measure. Pinch strength is measured at 3, 6, and 12 months. The first measurement is performed at both sides.

COMPLICATIONS

- Conservative treatment: pressure ulcers, neuropraxia or injury to the sensory superficial branches of radial nerve, arthrosis, chronic instability or limited function.
- Perioperative: vascular damage, nerve or tendon laceration.

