- Postoperative: surgical site infection, repeat operation, pressure ulcers, neuropraxia or injury to the sensory superficial branches of radial nerve, arthrosis, chronic instability or limited function.

Peri- and postoperative complications will be recorded according to tthe Clavien-Dindo Classification for hand surgery. Repeat operation and subsequent description of the additional treatment method will be reported.

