6.9 AEs and SAEs

6.9.1 Adverse events (AEs)

Adverse events are defined as any undesirable experience occurring to a subject during the study, whether or not considered related to the trial procedure or the intervention, conservative treatment. All adverse events reported spontaneously by the subject or observed by the investigator or his staff will be recorded.

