7. STATISTICAL ANALYSIS

Data will be analyzed following intention-to-treat. Categorical variables will be presented as counts and percentages and continuous variables as median and interquartile ranges or mean and standard deviation based on the normality of the data. Differences in characteristics between groups will be compared using Fisher exact and Pearson's χ^2 tests for categorical variables, and Wilcoxon rank sum tests and unpaired t test will be used for continuous variables, where appropriate.

We will conduct a linear regression analysis for longitudinal data (i.e. a mixed model) in which we correct for relevant prognostic factors (age, sex, time between trauma and definite treatment, duration of hand therapy) and baseline scores of the Michigan Hand Questionnaire. In an additional step, we will correct for surgeons depending on the number of treating surgeons as well as the number of patients per treating surgeon. Results will be presented as differences between treatment and control with 95% Confidence intervals. The intervention will be labeled as non-inferior when the noninferiority margin of 8 lies outside the 95% CI of this difference, regarding the Michigan Hand Questionnaire measured at 6 months as our primary endpoint. In case missing data did not happen randomly, but was related to specific factors (e.g. more missing data for men than for women), we will correct for this. In an additional analysis, the absolute MHQ scores at 6 months will be adjusted for differences in baseline MHQ scores between the intervention and control group. The secondary outcomes: PSFS, EQ5D, ROM, Kapandji score, grip strength, pinch strength and pain will be analyzed in a similar manner. Differences between the two treatment groups in complication rates will be analyzed using the Chi-square test or the Fischer's Exact test (in case the expected incidence was less than five).

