If the null hypothesis in this study of nonoperative treatment not being clinically non-inferior at six months is not rejected, but indeed lower costs are associated with nonoperative treatment, then incremental cost-effectiveness ratios will be calculated as the extra savings per extra unit in MHQ score lost or the extra savings per additional QALY lost. If the null hypothesis is rejected, a costs analysis and an outcome analysis will be done as distinct partial economic evaluations. The time horizon will be 12 months. It is expected that effects and costs beyond 12 months are similar for both treatment strategies and that a lifetime time horizon is redundant.

Differences between groups will be assessed after correction for bias and using accelerate non-parametric bootstrapping to account for sampling variability, generating 5,000 replications. Results will be presented graphically by cost-effectiveness planes. Cost-effectiveness acceptability curves will be drawn for various levels of willingness-to-pay per QALY up to €50,000, because higher levels cannot be justified by the maximum observable disease burden in this target group of patients. A scenario analysis will be applied by excluding the productivity losses following sick leave. Subgroup analyses will be performed for patients with a paid job.

Missing cost and effect data will be imputed using multiple imputation according to the MICE algorithm developed by van Buuren. Rubin's rules will be used to pool the results from the different multiply imputed databases. [14]

Measurement and valuation of costs

We will gather data on the use of resources and the related costs regarding health care (e.g. medical specialist, hand-physiotherapist, treatment of complications), productivity losses (absenteeism (sick leave) and presenteeism (lowered efficiency while at work due to sick leave from work and lowered productivity while a work)) and out-of-pocket

V7 01-02-2024 25 of 30

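### Chronic instability is a compared complication but has no definition and no scheduled stability test after week 2 (cast arm) or after the pre-surgery inclusion visit (surgery arm)

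*Protocol*

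**What the plan says.** **Complications.** Section 6.1.2 gives the list for non-operative treatment as "Conservative treatment: pressure ulcers, neuropraxia or injury to the sensory superficial branches of radial nerve, arthrosis, chronic instability or limited function". The postoperative list ends with the same items: "arthrosis, chronic instability or limited function". None of them has a threshold or a time point. A recording classification is named only for peri- and postoperative complications. Section 7 compares complication rates with a chi-square or Fisher exact test.

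**Stability testing.** Section 4.2 defines the injury by a radial stress test: no firm endpoint, together with either "at least more than 35 degrees of laxity in the MCP joint, measured with the MCP joint in 30 degrees of flexion" or a side-to-side difference above 15 degrees. Section 5.1 has the surgeon perform this test at the first outpatient visit in both arms. In the cast arm there is one repeat, at 2 weeks: "Laxity of the MCP joint is re-examined by a hand surgeon". No later test is named in either arm.

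**Follow-up.** Both arms return at 4 weeks, 3, 6 and 12 months for physical examination and surveys. The clinician measures in section 6.1.2 are range of motion, Kapandji score, grip strength and pinch strength. The analysis list in section 7 matches: "The secondary outcomes: PSFS, EQ5D, ROM, Kapandji score, grip strength, pinch strength and pain will be analyzed in a similar manner".

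**Other capture.** Section 6.9.1 states: "All adverse events reported spontaneously by the subject or observed by the investigator or his staff will be recorded". Section 6.2 says that blinding of patients and surgeons is not possible. Section 5.2 accepts residual laxity as a possible result of non-operative healing: "Although the ligament sometimes heals with slight laxity, there is no evidence for any benefits to surgery that outweigh the risks of nonoperative treatment".

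**The concern.** The trial asks whether a completely ruptured ligament can first be left unoperated. Chronic instability is the listed complication most directly tied to that injury, and the protocol itself treats a firm endpoint at 2 weeks as evidence of adequate healing. Yet a rate that section 7 will test between arms has no case definition, and no planned examination establishes it.

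The arms also differ in how they are examined. The cast arm has one stress test after treatment starts; the surgery arm has none after the repair. With open treatment, whether anyone stresses the joint at a later visit, and in which patients, is left to the examiner. An examination that was never made cannot be recovered at analysis, so this belongs in the protocol rather than in a later analysis plan.

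Arthrosis has a similar problem. It is in the compared list, but no follow-up imaging is planned that would ascertain it equally in both arms.

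**Working it through.** **1. Schedule set against the complication list** (sections 4.2, 5.1, 6.1.2, 6.3)

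| Time | Cast arm | Surgery arm |
|---|---|---|
| Inclusion | stress test | stress test (before surgery) |
| 2 weeks | stress test | none named |
| 4 weeks | range of motion, Kapandji | range of motion, Kapandji |
| 3, 6, 12 months | range of motion, Kapandji, grip, pinch | range of motion, Kapandji, grip, pinch |

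Range of motion is defined as flexion and extension of the MCP and IP joints and palmar abduction of the CMC joint. Neither that nor Kapandji, grip or pinch tests radial opening or the endpoint. The readable part of Figure 2 agrees, but the table is broken in extraction and little weight rests on it. For cast-arm patients who switch to surgery after the 2-week visit (about 1 in 10 expected), the last scheduled test also precedes their operation.

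**2. Patient numbers.** The protocol has no figure for instability to reproduce. The only number borrowed is 57 per arm from section 4.4, and it checks. With margin 8, SD 15, one-sided 0.025 and 80% power, the normal formula 2(1.96 + 0.84)² × 15² / 8² gives about 55.1, so 56 per arm. The noncentral t calculation gives power 0.799 at 56 and 0.806 at 57.

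**3. Illustration only.** All instability rates and detection shares below are assumptions.

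*Equal detection share s in both arms.* The observed difference is s × (p_cast − p_surgery). For 10% and 2%, it is 8.0 points at s = 1, 4.0 at s = 0.5 and 2.4 at s = 0.3.

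Power with n = 57 per arm, two-sided 0.05, is Φ[(d − 1.96√(2p̄(1−p̄)/n)) / √((p₁(1−p₁) + p₂(1−p₂))/n)], with p₁ and p₂ already multiplied by s, d their difference and p̄ their mean:

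| True rates (surgery, cast) | s = 1 | s = 0.75 | s = 0.5 |
|---|---|---|---|
| 2%, 10% | 0.44 | 0.34 | 0.24 |
| 2%, 15% | 0.71 | 0.57 | 0.40 |
| 2%, 20% | 0.88 | 0.75 | 0.56 |

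The approximation is rough: 57 × 0.02 is 1.1 expected events in the surgery arm.

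*Unequal detection.* Take a true rate of 10% in both arms. If 75% of cases are found in the cast arm and 50% in the surgery arm, the observed rates are 7.5% and 5.0%, a spurious +2.5 points against cast. Reverse the shares and it is −2.5 points. The sign depends on who looks harder, and the protocol does not fix that.

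**The case against.** **Detection is not left to chance.** A reader might infer that instability would be found only by accident. The documents do not support that. Both arms attend four later visits with physical examination, complications are a stated secondary objective, observed adverse events are recorded and repeat operations are reported. MHQ, PSFS, pain and pinch strength may also reflect symptomatic instability. This stands: detection is unstandardised, not accidental. But those measures are not specific to instability and cannot supply the rate that section 7 compares.

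**It is not shown to be the main harm.** The protocol ranks no harms, and section 5.2 speaks only of slight laxity. Choosing a patient-reported primary endpoint is legitimate.

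**It does not tilt the trial towards non-inferiority.** A reader might infer that under-recording favours cast. Non-inferiority is decided on MHQ at 6 months alone, and complications have no role in it. Nor is the direction known: equal under-detection shrinks a true difference, whereas closer scrutiny of unoperated thumbs would inflate the cast-arm rate.

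**It does not overturn the 12-month horizon.** The economic section says "It is expected that effects and costs beyond 12 months are similar for both treatment strategies and that a lifetime time horizon is redundant". That is already worded as an expectation about effects and costs, and MHQ, EQ-5D and costs are all collected at 12 months. Residual laxity would not settle it.

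**Arthrosis could still be recorded** if diagnosed in routine care, since patient records are a data source. That is fair. What is missing is equal ascertainment.

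**Definitions may sit in the CRF or analysis plan, and measurements follow an external outcome set.** A definition could indeed sit there, but it would not schedule an examination. Section 6.1.2 cites the external set for how measurements are performed, not to add any; the set itself cannot be checked here.

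**Conclusion.** The point holds in a limited form. Chronic instability is listed in both arms and falls within a tested comparison, but it has no definition. It also has no scheduled stability test after week 2 in the cast arm or after the pre-surgery inclusion visit in the surgery arm. That comparison is unreliable and could be biased either way.

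The size cannot be derived, because the documents give no instability rate; the power and bias figures above only show what the assumed rates would imply. Even with full ascertainment the trial is not powered for this outcome. At 10% and 2% the Wald half-width is 1.96√((0.10 × 0.90 + 0.02 × 0.98)/57) = 8.6 points around a difference of 8, itself a rough figure with so few events. The primary analysis and the sample size are untouched. This is a cheap improvement that should be made, not a flaw that threatens the main conclusion.

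**What to change.** - **Measure.** At the existing 6- and 12-month visits, in both arms, record the section 4.2 stress test on both thumbs: firm endpoint yes or no, and degrees of laxity at the joint position stated there. The uninjured thumb is needed because one of the criteria is a side-to-side difference.
- **Define.** For analysis, call chronic instability present when the section 4.2 criteria are still met at those visits. This classifies an outcome; it sets no treatment rule.
- **Analyse.** Add laxity to the secondary outcomes in section 6.1.2, Figure 2 and section 7. Reporting degrees as well as the yes/no item keeps slight laxity with a firm endpoint visible.
- **Arthrosis.** Report it descriptively as diagnosed in routine care, outside the tested comparison. No new imaging is needed.

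**Cost.** A protocol and CRF amendment, a little extra examination time and brief discomfort for patients. Patients already past a visit will lack that value. Assessment stays unblinded, so the change standardises who is tested and how, but does not remove observer bias.

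### Complications have no common definition or grading across the arms: a repeat operation is listed after surgery, but a later unplanned operation after cast treatment has no item, and only operative complications are graded

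*Protocol*

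**What the plan says.** Protocol section 6.1.2 (Complications) gives three lists, keyed to the treatment received:

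- The list for cast treatment reads "Conservative treatment: pressure ulcers, neuropraxia or injury to the sensory superficial branches of radial nerve, arthrosis, chronic instability or limited function".
- The list for the operation itself names damage to vessels, nerves and tendons.
- The list for the period after surgery begins "Postoperative: surgical site infection, repeat operation, pressure ulcers, neuropraxia or injury to the sensory superficial branches of radial nerve"; its remaining items match the end of the cast list.

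On grading, the section says "Peri- and postoperative complications will be recorded according to" a named scale, Clavien-Dindo. No scale is named for complications of cast treatment. A further sentence promises a report on second operations: "Repeat operation and subsequent description of the additional treatment method will be reported".

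Section 7 analyses the data by intention-to-treat and states: "Differences between the two treatment groups in complication rates will be analyzed using the Chi-square test or the Fischer's Exact test". Complications are among the secondary objectives in section 2.

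Section 5.1 makes surgery a planned step of the cast strategy when the 2-week examination finds no firm endpoint or leaves doubt. The Summary expects this in about 1 in 10 cast patients.

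**The concern.** A between-group test of complication rates needs the same events to count in both groups. Surgical site infection belongs naturally to an operative list. An unplanned operation does not, because either strategy can fail and lead to one. After surgery, a further operation is a listed event. After cast treatment that passed the 2-week check, a later operation on the thumb is a first operation, so it is not literally a repeat one. Neither the cast list nor the sentence on reporting repeat operations clearly covers it.

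The same pressure ulcer or nerve injury is graded if it follows surgery and ungraded if it follows cast treatment alone. A reader of the final report could then compare how often complications occurred, but not how serious they were.

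At stake is the safety comparison that would accompany a non-inferiority claim for cast. If it leaves out a foreseeable form of cast failure, it can make cast look better than it is.

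**Working it through.** **Arm size.** Section 4.4 gives 114 × 1.10 = 125.4, rounded up to 126. Half is 63 per arm, on average under simple randomisation. This agrees with the protocol, and no stated number is in dispute.

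**Planned conversions.** 63 × 0.10 = 6.3, about 6 cast patients. The two series in section 5.2 had secondary surgery in 3/32 = 9.4% and 6/40 = 15%. The protocol does not say how much of that surgery would fall after a 2-week check, so these figures show that late surgery is foreseeable without giving its rate.

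**The lists side by side.**

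| Item | After cast | After surgery |
|---|---|---|
| Pressure ulcer; nerve branch injury; arthrosis; instability or loss of function | listed, no scale | listed, Clavien-Dindo |
| Infection; vascular, nerve or tendon damage at operation | not listed | listed, Clavien-Dindo |
| Further or unplanned operation on the thumb | no item | repeat operation listed, Clavien-Dindo |
| Re-rupture | not listed | not listed |

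**Illustration of size.** The rates here are assumptions, because the protocol gives none. Let

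- c = proportion with another complication, equal in both arms: 5% to 10%;
- r = proportion with an unplanned operation, equal in both arms and independent of c: 1% to 5%;
- q = proportion of cast patients converted at 2 weeks: 10%. After conversion they fall under the operative lists, so their repeat operations count in the cast arm.

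Lists as written, with late operations after cast uncounted:

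- surgery arm = c + (1 − c) × r
- cast arm = c + (1 − c) × q × r
- cast minus surgery = −(1 − c) × (1 − q) × r

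| c | r | Cast minus surgery | Patients of 63 |
|---|---|---|---|
| 5% | 1% | −0.95 × 0.90 × 1 = −0.9 points | 0.5 |
| 5% | 3% | −0.95 × 0.90 × 3 = −2.6 points | 1.6 |
| 5% | 5% | −0.95 × 0.90 × 5 = −4.3 points | 2.7 |
| 10% | 5% | −0.90 × 0.90 × 5 = −4.1 points | 2.6 |

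With one common item, both arms equal c + (1 − c) × r and the difference is 0. The whole gap in the table therefore comes from the definition. If every late operation after cast were already recorded under instability or loss of function, the gap would also be 0. The range under these assumptions is 0 to about 4.3 points.

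**Scale of the test.** With 57 evaluable patients per arm, Fisher's exact test has only about 27% power for 5% against 14.5%. The comparison will be read mainly from the counts, so their definition matters more than the p-value.

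**The case against.** Much of the case on the other side stands.

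- **The 2-week operation is planned.** Section 5.1 builds it into the cast strategy, and section 6.7 accepts its risk because every control patient has such an operation upfront. A converted patient's first operation corresponds to the control patient's primary operation, which is not a complication either. Leaving conversions out of the complication count is defensible.
- **Intention-to-treat works against a simple bias.** Operative complications of converted patients, including repeat operations, count in the cast arm.
- **Late cast failure need not go unrecorded.** It may be entered as lasting instability or loss of function. Section 6.9.1 records all adverse events, and the exploratory analysis in section 7 requires everyone who eventually had surgery to be identified.
- **Grading does not enter the planned test.** Ungraded events still count in a rate.

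A reader might infer more: that the comparison is settled in favour of cast, or that its direction would reverse if operations after a failed cast were counted. With c = 5%, r = 3% and q = 10%, and repeat operations in converted patients left aside, counting every conversion moves cast minus surgery from −0.95 × 3 = −2.85 to 0.95 × (10 − 3) = +6.65 points. That reversal depends on treating every planned conversion as a complication and on assumed rates, and the documents support neither. A reader might also point to re-rupture, since the 2-week stress examination is part of the cast protocol. But re-rupture is on neither list, and section 5.1 says: "The chance that re-examination at 2 weeks will induce a re-rupture or a Stener Lesion is close to zero". It shows no asymmetry.

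These arguments do not supply a common item for unplanned surgery after cast. Adverse event recording does not close the gap, because section 7 tests complications and section 6.9.2 excludes elective admissions from serious adverse events. How events are tabulated may be left to the statistical analysis plan, but the protocol itself fixes what is listed and graded.

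**Conclusion.** The concern holds in a limited form. The protocol compares complication rates between randomised groups without a common definition of unplanned secondary surgery and without a common grading scale. The omission can favour cast, and severity cannot be compared between arms.

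Size and direction in the actual data cannot be derived from the protocol. The illustrative gap of 0 to about 4 points rests on equal and independent unplanned-surgery rates of 1% to 5%, other complications at 5% to 10%, and 10% conversion. It shrinks to nothing if sites record late cast failures under the existing items. Settled bias, or a reversed result, is not established.

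The MHQ endpoint at 6 months, the non-inferiority margin and the sample size are untouched. This is a correction to one secondary comparison. It is worth making because an event that sites do not record or grade may not be recoverable at analysis.

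**What to change.** In section 6.1.2, replace the treatment-specific lists with one complication list for every randomised patient, analysed by assigned arm. Include an item for any unplanned or secondary operation on the study thumb, counted the same way in both arms. Name one grading scale and apply it to every listed complication, whether it follows cast or surgery.

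In section 7, state that the comparison uses this list. Report planned 2-week conversions on a separate line by arm, not as complications; about 6 of 63 are expected in the cast arm. Complications of the conversion operation itself continue to count in the cast arm.

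The cost is small: changes to protocol and case report form wording and one extra table row. The downside is that the cast arm's reported rate may be less favourable.
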